The **purpose** of this study will be to generate the data required to thoroughly validate the ability of plague LFI assay to accurately diagnose human infections with *Y. pestis*. These validation data will eventually be presented to the FDA (along with data from other types of studies not from human subjects) to seek approval for commercial license.

STUDY OBJECTIVE

The objective will be to validate this assay on the capillary blood of humans suspected to have plague.

SPECIFIC AIMS

The specific aims of this study are to enroll up to 300 participants who present clinical signs of illness based on specific inclusion criteria. We will collect two types of blood samples from enrolled participants 1) capillary blood from a finger prick and 2) venous blood. The capillary blood will be used for direct testing on the LFI assay and the venous blood will be used to perform independent validations using FDA approved methods. This study is designed as a correlation study to understand 1) how LFI assay results compare with results from traditional diagnostic methods based on DNA detection methods and bacterial culture isolate and 2) effectiveness of capillary blood to serve as a diagnostic clinical sample as compared with traditional biological samples (venous blood, bubo and sputum). The study is designed to evaluate the outcome of LFI (*SMART™-PRT*, New Horizons Diagnostics Corp.

<https://www.nhdiag.com/index.htm>) and how LFI results correlate with the standard plague diagnostics methods used in Madagascar and two other FDA-approved methods. We are not examining the relationship between the results of the LFI and health outcomes of the participants. Decision of participant's medical treatment is solely based on the clinical judgment of the physician and guidelines set forth by Madagascar National Plague Control Program (PNLP). All participants who are tested by LFI will have received medical treatment prior to the start of the study and the continuation of their medical treatment is guided by PNLN and physician judgment only.

BACKGROUND

Yersinia pestis, which causes the disease plague, is ecologically established in rodent populations worldwide, including on all continents except Australia and Antarctica. Plague is a rapidly progressing highly feared infectious disease that historically was responsible for the deaths of millions world-wide due to natural outbreaks during three major pandemics. Within the last century, several nation states developed plague as a biological weapon and the US government currently lists *Y. pestis* as a potential bioweapon (1) that could be used against US war fighters. As a natural disease, plague continues to be a threat in modern times with the World Health Organization (WHO) classifying it as a re-emerging infectious disease . Human plague outbreaks occur naturally on an annual basis worldwide with the vast majority of cases (4,5) located in rural remote low-resource settings of Madagascar, an island nation off the east coast of Africa. Madagascar has more human plague cases than any other country in the world. In 2015 alone, WHO reported 85.93% of global cases came from Madagascar (2). Over a five-

year period, there have been more than 3,500 suspected human plague cases in Madagascar ([name] et al., unpubl).

In nature, humans acquire plague by being bitten by fleas carrying *Y. pestis*. The bacterium travels to the nearest lymph node (LN) from the wound site and causes LN swelling, known as a bubo (hence, bubonic plague) within 3-6 days post infection with a 50%-70% mortality rate if untreated. If bubonic plague is not medically treated, it can further progress to infect the lungs (pneumonic plague) for which person to person transmission can ensue. Pneumonic plague, is a rapidly progressing disease (1-3 days) with 100% mortality rate; for this reason, aerosolized *Y. pestis* is of concern as a potential biological weapon. Importantly, there are no licensed vaccines currently available for plague, so antibiotics are the only means to medically defeat this disease. Key to preventing mortality and further transmission in rural settings is the ability to rapidly diagnose at the very early acute phase of the disease. Such a diagnostic assay would need to be highly simple and usable in a low-resource setting to effectively service the human populations most affected (local rural inhabitants and possibly warfighters).

The existing rapid diagnostic assay generally relies on detection of the F1 antigen of *Y. pestis* or serodiagnosis of anti-F1 antibody (6). A rapid assay, F1RDT (3) is not licensed for commercial use but is used in low-resource settings worldwide. This assay uses non-blood clinical samples (bubo aspirates and sputum) to diagnose. Procuring bubo aspirate for diagnosis requires an invasive collection procedure that is significantly more painful than blood sample collection. The research here aims to evaluate the diagnostic effectiveness of a blood-based rapid diagnostic assay. This is a US-developed assay based on a Lateral Flow ImmunoAssay (LFI) design concept similar to a home pregnancy test. The biological sample target is capillary blood from a finger prick. The simplicity of design enables this assay to be used in low-resource settings. We will evaluate the expression levels two *Y. pestis* proteins in the capillary blood of humans suspected to have plague and determine how these levels correlate with results from traditional diagnostic assays.

Lay Summary: Plague is a deadly but highly treatable disease caused by the bacterium *Y. pestis*. Due to the historical development of *Y. pestis* as a bioweapon by several nation states, it is listed by the US as a potential bioweapon that could be used against US warfighters. Although this bacterium is ecologically established worldwide, it mostly affects impoverished people who live in rural low-resource areas of Madagascar. Plague is acquired directly from bites of infected fleas but, if left untreated, it can progress to the highly lethal pneumonic form that can result in human to human transmission. With the dangers of pneumonic plague in the context of both natural outbreak and as a bioweapon used against warfighter, the goal of this study is to investigate a diagnostic test that is able to rapidly and locally diagnose this disease in low-resource settings. This study aims to evaluate a US-developed new LFI assay intended for capillary blood to diagnose humans infected with *Y. pestis*. We will rigorously validate with assay on human populations from active plague sites and correlate the results with the results of paired clinical samples used in standard medical workup using existing diagnostics tests.

RESPONSIBLE INSTITUTES

Brimrose is the sponsor for this clinical trial study and will be the entity to manufacture the LFI device. [name], Director Biotechnology Division at Brimrose, will be responsible for overseeing the device component of this entire study. He will take the data generated from this study to the FDA for clearance request. Northern Arizona University (NAU) is the lead institute for overseeing the field work conducted in Madagascar which involve enrolling human subjects suspect to be plague positive and test the LFI device on their clinical samples. NAU has partnered with Institut Pasteur de Madagascar (IPM) to perform this field work. Madagascar is the region with the most active plague site in the world documented by the WHO and, for this, IPM is the world's expert on managing human plague outbreaks, and they have the field work expertise necessary to successfully validate this LFI assay. The technical expertise for the LFI assay will come from the Naval Health Research Center (NHRC). They will provide quality training and will serve as a technical liaison. As the lead institute, NAU (<https://in.nau.edu/pmi/>) will oversee the work performed by our International Partner (IPM) and will coordinate the training of IPM personnel. [name] will be responsible for the global scientific direction for the field work and [name] will be responsible for the coordination of the collaboration for the human subject research that occur in Madagascar.

International Partner: IPM is the lead plague research organization in Madagascar and has collaborated with NAU on several previous plague studies in Madagascar. Diagnosing and reporting of human suspect plague cases is mandatory by Madagascar national law under Plague National Control Program (PNLP). The Madagascar Ministry of Public Health (MMPH), as part of PNL, requires declaration of all suspected human plague cases and mandates the collection of biological samples (sputum and bubo aspirates, but not blood) from these cases as part of the confirmation procedure. Human plague outbreaks primarily occur in rural low-resource settings. These cases are treated at local rural health centers located throughout Madagascar. Local physicians collect clinical specimens (bubo aspirates and/or sputum), which are then transported to IPM, located in Antananarivo, where sample workup is performed. IPM facility serves as the national plague reference laboratory, and has stored 90% of human samples and bacterial isolates from recent cases across five years. Drs. [name] (head of the plague unit – Science officer) and [name] (senior scientist - PI) are key IPM personnel. Personnel conducting the field study include: [name] and [name]. All the IPM field investigators are medically and/or paramedically trained and have ≥ 8 years of field experience. IPM personnel, [name], will serve as study coordinator and will handle highly sensitive medical information. Because IPM is charged by the Madagascar government to oversee all operations involved with managing active plague outbreaks, IPM personnel are well connected with rural local public health officials. They communicate regularly with rural health officials to provide consultations (via email and cell phone) and support (medical supplies and personnel).

MANAGEMENT PLAN

The Directors and PIs at each of the participating institutions are well experienced and will be responsible for their respective entity's participation in the project. [name] from Brimrose will serve as the sponsor for this clinical trial study. [name] will serve as the overall PI (and co-PI for the human subjects research) and will be responsible for the global scientific direction

and coordination of the collaboration for the field work in Madagascar. [name] will serve as PI for the human subjects research component for this project. The PIs of the respective institutions will meet bi monthly by videoconference and also regularly communicate via email. In addition, NAU, and IPM will meet together in person annually or biannually at agreed location site once the COVID pandemic subsides.

TRAINING ON LFI ASSAY IMPLEMENTATION

A formal training on LFI device will be given. The NAU group will meet with the Naval Health Research Center (NHRC) to develop LFI assay protocol and train on the LFI assay. NHRC will provide training for the assay and will serve as a technical liaison for both NAU and IPM, with NAU overseeing training of IPM personnel. NHRC will ensure that overall protocols developed by NAU are being implemented correctly. This training includes proper use of the LFI assay, accuracy in reading of LFI results, and proper method of data collection. NHRC will provide NAU and IPM with onsite training at both facilities (NAU and IPM) at a sufficient timing to meet the requirements of the statement of work.

FIELD INVESTIGATION PROTOCOL

IPM has developed a field sampling protocol which closely mirror those from past field missions conducted for retrospective plague investigations. IPM and NAU will work together to finalize the field sampling protocol that will involve enrolling up to 300 participants across two plague seasons (Table 1). Five IPM personnel with field mission experience were trained according to IRB requirements.

Timeline of study activity: Human plague in Madagascar has a distinct seasonal component and is associated with specific environmental conditions. The human plague season typically starts to take off in September, peaks from October to January, and tapers off in March.

Table 1: Timeline for the study divided across three performance periods

(Base period = 18 months; Option Period 1 (OP1) = 12 months; Option Period 2 (OP2) = 6 months). Months are aligned with plague seasons, performance periods and study activities.

Month	Plague Season	Period	Study Activity
Dec-19	2019-2020 plague season	Base	
Jan-20	2019-2020 plague season	Base	Get Human Subjects Approval in place (NAU IRB, IPM IRB)
Feb-20	2019-2020 plague season	Base	
Mar-20	2019-2020 plague season	Base	
Apr-20	2019-2020 plague season	Base	
May-20		Base	
Jun-20		Base	
Jul-20		Base	
Aug-20	2020-2021 plague season	Base	1. Consent and Enroll; 2. LFI Testing and confirmatory testing
Sep-20	2020-2021 plague season	Base	
Oct-20	2020-2021 plague season	Base	
Nov-20	2020-2021 plague season	Base	
Dec-20	2020-2021 plague season	Base	
Jan-21	2020-2021 plague season	Base	
Feb-21	2020-2021 plague season	Base	
Mar-21	2020-2021 plague season	Base	
Apr-21	2020-2021 plague season	Base	
May-21		Base	
Jun-21		OP1	Confirmatory testing
Jul-21		OP1	
Aug-21	2021-2022 plague season	OP1	
Sep-21	2021-2022 plague season	OP1	1. Consent and Enroll; 2. LFI Testing and confirmatory testing
Oct-21	2021-2022 plague season	OP1	
Nov-21	2021-2022 plague season	OP1	
Dec-21	2021-2022 plague season	OP1	
Jan-22	2021-2022 plague season	OP1	
Feb-22	2021-2022 plague season	OP1	
Mar-22	2021-2022 plague season	OP1	
Apr-22	2021-2022 plague season	OP1	
May-22		OP1	
Jun-22		OP2	Confirmatory testing
Jul-22		OP2	
Aug-22		OP2	
Sep-22		OP2	
Oct-22		OP2	
Nov-22		OP2	

Location: The study will be carried out mostly in endemic plague outbreaks regions in Madagascar (i.e., the Central Highlands region) but can extend to any region in Madagascar where local clinical health officials report human plague.

Study population: Active plague sites tend to be located in low resource rural settings. The study population will be comprised of local people presenting signs of illness consistent with plague. They will be recruited at rural health centers located throughout Madagascar. The Madagascar Ministry of Public Health requires declaration of all suspected human plague cases and mandates the collection of biological samples (sputum and/ or bubo aspirates) from these cases as part of the medical workup for official confirmation. Our proposal will work within this existing mandatory confirmation and reporting system to obtain the requisite enrollment number. Since blood is a novel biological sample for plague diagnostics, we will include a traditional clinical sample type as a positive control for plague detection. We will test the LFI on residual de-identified clinical samples (bubo and/or sputum) from participants who are enrolled in our study. This would thoroughly document the diagnostic capabilities of the LFI assay as compared to paired capillary blood.

We plan to enroll up to 300 participants across the entire study which encompasses two plague seasons (Aug 2020-March 2021; Aug 2021-March 2022). We aim to enroll at least 150 participants per plague season but if the opportunity presents to enroll more within the first plague season, then we will proceed to enroll up to 300 participants.

- The **inclusion criteria** for this study
 - Adults 18 to 75 years old (male and female)
 - Be able to receive and give verbal communication
 - Children 5 to 17 years old (vulnerable population)
 - Parents or legal guardian be available to give permission.
 - Parents or legal guardian to consent for children (5-6 years)
 - Identified as a suspect human plague case by the local medical professional

 - Will include at least one of the following symptoms:
 - For bubonic plague: High fever, chills, and/or the presence of a painful bubo
 - For pneumonic plague: High fever, chills, cough for less than 5 days, bloody sputum, and/or chest pains.
 - Patients may be recruited from both plague surveillance program and non-plague surveillance programs.
 - For this study, patients from the plague surveillance program will have higher priority for enrollment than patients from the non-plague surveillance programs.

- The **exclusion criteria** for this study
 - Children under the age of 5 years old
 - Children between the age of 5 years to 17 years without a parent or legal guardian
 - Not compliant with the study procedure (blood sampling)

Adults 18 to 75 years old (male and female), Children 5 to 17 years old with parent or legal guardian, Malagasy nationals across all ethnic groups can participate. This study does not exclude pregnant women but they are not considered vulnerable population because their pregnancy status is not a selection criterion. For this reason, Appendix B is not included in this application.

Participants will initially learn about the study from their physician during their medical consultation. They will then receive an information sheet by the physician who will then be referred to an IPM personnel to receive more information about the study.

When will recruitment occur? Recruitment will most likely occur during the regular plague season (Aug 2020-April 2021 and Aug 2021-April 2022) when plague activity is high but it can happen any time of the year as sporadic cases can arise outside of the normal season. Local physicians will alert IPM of a suspect plague case at their health center. IPM personnel will be dispatched to this local health center and begin the informing, consenting, and enrolling process.

Where will recruitment take place? The recruitment will take place at the site of regional and local health centers throughout Madagascar where local people seek medical assistance. It is local practice for IPM research personnel to visit these healthcare facilities to provide additional medical assistance (during outbreaks) at the invitation of the local physicians and perform plague investigations to fulfill Malagasy government mandates.

Identifying partnering healthcare centers. During the low plague season (May – Aug), IPM will contact the local physicians from regional health center to inform them of this study. Physicians will learn about the study's purpose, design, and the referral role for which they would serve. From these communications, IPM will know in advance which health centers plan to participate.

Identifying suspect plague case and providing immediate medical treatment. When the local physician has identified a suspect plague case based on clinical presentation, he/she will perform the national protocol for declaring suspect plague case. This includes collecting medical workup samples (sputum and/or bubo aspirates) and completing a TLO declaration form. The sample and TLO form are to be given to IPM for medical workup for official confirmation, irrespective if the patient enrolls in the study. The physician will then provide standard medical care according to PNLP. This includes administration of antibiotics. Blood collection is not part of the standard medical workup.

Role of physicians as providing referrals. The physician is not part of the research but will provide prospective subjects with information about the research (which, in this case, includes the information section of the informed consent document but will not obtain subjects' consent for the research or act as representatives of the investigators. This practice is in alignment with guidance on engagement described here: <https://www.hhs.gov/ohrp/regulations-and-policy/guidance/guidance-on-engagement-of-institutions/index.html>. After the start of medical

treatment, the local physician will alert the Plague-IPM Unit of suspect plague case(s) at their health center. IPM will immediately dispatch field investigators who will arrive as soon as possible. The physician will give a leaflet to the patient that will provide information about the study conducted by IPM. If the patient is illiterate, then the physician will read the leaflet aloud. The local physician will then refer them to IPM personnel for more information. This is a process approved by the local ethics committee. The physician will not participate in the consenting and enrollment process but rather refer patients to the study. Medical treatment already started before introduction of the study and will continue regardless of study enrollment status.

Consenting participants. The informing, consenting, enrolling, and sample collection process will be performed in a room at the local health center and will require two to three hours total. If the participant meets the inclusion criteria, the potential participant will undergo the consenting process. He/she will meet face to face with an IPM personnel who will verbally take them through the study information (the objectives of the study, proposal to participate in the study, and the type of sample to be taken – as laid out in the flyer leaflet. He/she will be provided a hard copy of the informed consent form that contains the signature and give them time for review. For those who are illiterate, the IPM personnel will verbally communicate the consent form information and the signature page at a language level that is understood by the participant. After confirming that each participant understands the nature and details of the study, they will be given the opportunity to ask questions and to receive answers. Part of this confirmation is to ensure they understand that entities outside of Madagascar may review their data records and health information (age, gender, location, clinical form of the disease, medical treatment). No identifiable information will be provided to outside entities. FDA and DoD are not specifically mentioned in the consent form due to a lack of familiarity of this organization for the typical participant in this study. After this comprehension check, each person will be asked if they would like to enroll in the study. To be enrolled, each participant must sign the informed consent form. For those who are illiterate, they will sign by marking an X or provide a finger print on the signature line. For minor children ages 5-17, the parents or legal guardian will sign the consent form to authorize permission. The minors ages 7-17 will provide assent by signing the assent form. For children ages 5-6, a parent or legal guardian signs the assent letter in their place. Two duplicate consent form (and assent form if applicable) will be signed, with one copy be given to the patient or parent / legal guardian and a second copy retained by IPM) for long-term storage for five years.

Post Enrollment Procedure. Once a participant is enrolled, the IPM personnel will assign a numeric code to represent, a unique identifier code (TLO #) to track data collected to preserve the participant confidentiality. Then the IPM personnel will measure the body temperature using an axillary thermometer and proceed to perform a one-time collection of two types of blood (venous and capillary) that will total less than 5 ml. This is equivalent to approximately one teaspoon of blood. Each blood sample type will be labeled with the participant's TLO #. Approximately 4 ml of venous blood will be drawn out of the vein of an arm into a storage tube designed for blood preservation and ~ 0.1 ml of capillary blood will be captured from a finger prick into a capillary tube. These blood collection procedures are done using standard medical

Diagnostic testing of biological samples. For the venous blood, these tests include two primary confirmation method (Table 3): 1) Real-time qPCR and 2) Culture for bacterial isolation. Venous blood samples will be processed for secondary confirmatory methods: 1) DNA testing using FilmArray NGDS Warrior Panel (FDA-approved), 2) testing for presence of plague antibodies, and 3) DNA analysis for genetic studies and genome discovery. FilmArray warrior panel will serve as one of several independent diagnostic confirmation methods to compare LFI results. The medical workup samples will be largely consumed for confirmation tests mandated by Madagascar law (Table 3 – gray highlights). Remaining residual amounts will be utilized to test on LFI and extract DNA for genetic studies.

Table 3: Four human specimen types collected in the field and their respective analytical fates. Each field sample will be tested directly or after further processing "Analyzed Sample". Each analytical fate is classified as the new device diagnostic test (LFI = Lateral Flow ImmunoAssay), primary confirmation (qPCR = DNA tests; Culture = bacterial isolate), and secondary confirmation (RDT = Rapid diagnostic test; ELISA = antibody detection in blood; FilmArray Warrior Panel PCR, canSNP = Genetic typing; WGS = Whole genome sequencing to discover novel regions). Region in gray indicate standard medical workup confirmatory testing mandated by Madagascar law. Region in black are tests not subject to IRB regulations due to the use of de-identified residual medical workup specimens.

Field Sample	Analyzed Sample	Work done at Madagascar						Work done at NAU - USA	
		LFI	2 target qPCR	Culture	IPM F1 RDT	ELISA	FilmArray	canSNPs	WGS
Capillary blood	Capillary blood	YES	-	-	-	-	-	-	-
Venous blood	Venous blood	-	-	YES	YES	-	YES	-	-
Venous blood	DNA extracted from venous blood	-	YES	-	-	-	-	YES	-
Venous blood	Sera obtained from venous blood	-	-	-	-	YES	-	-	-
Venous blood	Isolate obtained from venous blood	-	-	-	-	-	-	-	-
Venous blood	DNA extracted from blood isolate	-	YES	-	-	-	-	YES	YES
Bubo aspirate	Bubo aspirate	YES	-	YES	YES	-	-	-	-
Bubo aspirate	DNA extracted from bubo aspirate	-	YES	-	-	-	-	YES	-
Bubo aspirate	Isolate obtained from bubo aspirate	-	-	-	-	-	-	-	-
Bubo aspirate	DNA extracted from bubo isolate	-	YES	-	-	-	-	YES	YES
Sputum sample	Sputum sample	YES	-	YES	YES	-	-	-	-
Sputum sample	DNA extracted from sputum sample	-	YES	-	-	-	-	YES	-
Sputum sample	Isolate obtained from sputum sample	-	-	-	-	-	-	-	-
Sputum sample	DNA extracted from sputum isolate	-	YES	-	-	-	-	YES	YES

Description of assay

- New investigative *in vitro* (outside of human) diagnostic assay: Lateral Flow ImmunoAssay (LFI) (Fig 1)
 - Not FDA approved

- This Madagascar study will inform decision on FDA clearance path for the LFI.
- Until FDA approval – the device risk determination was determined as non-significant by the sponsor (Brimrose) and the IRB of record (NAU).
- Biological Sample Type and Volume:
 - Human biological samples (capillary blood, sputum, bubo aspirate)
 - Volume (30 ul - 50 ul) is equivalent to 3-5 eye drops of liquid
- Device characteristics: Design concept is very similar to a home pregnancy test
 - Result will be read by eye after 15 minutes
 - This assay was developed by New Horizons Diagnostics Corp. and targets two plague proteins, F1 and LcrV. (<https://www.nhdiag.com>)
 - The F1 protein is well characterized but the characteristics of LcrV protein in terms of expression and stability in the context of human infection is not known.
 - Results from this study can provide knowledge in this area.

[figure not shown]

Figure 1. New Horizons Diagnostics Corp has developed a rapid point-of-care lateral flow immunoassay (LFI) to diagnose plague infections. This assay (SMART™-PRT) is a multiplex LFI capable of detecting two *Y. pestis* antigens; F1 and LcrV. The picture illustrates results with laboratory-purified antigens (top) and control (bottom). The test requires a single drop of blood from a finger stick and is read in 15 minutes.

Data Analysis:

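### Does recruiting from undefined non-plague surveillance programs let people who are not suspect cases into the accuracy estimates?

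*Protocol*

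**What the plan says.** The inclusion criteria, in the Field Investigation Protocol, require that a participant be "Identified as a suspect human plague case by the local medical professional" and have at least one symptom from a bubonic or pneumonic list. In the same list stands "Patients may be recruited from both plague surveillance program and non-plague surveillance programs", followed by the rule that "patients from the plague surveillance program will have higher priority for enrollment than patients from the non-plague surveillance programs". The non-plague programs are not defined anywhere, and no number or share is set for them. Enrolment from all sources together is limited to 300, with an aim of at least 150 per season.

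The other sections speak of suspects only:

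- Study Objective: "The objective will be to validate this assay on the capillary blood of humans suspected to have plague".
- Specific Aims: "All participants who are tested by LFI will have received medical treatment prior to the start of the study".
- Study population: "Our proposal will work within this existing mandatory confirmation and reporting system to obtain the requisite enrollment number".
- When will recruitment occur: "Local physicians will alert IPM of a suspect plague case at their health center".
- Role of physicians: "Medical treatment already started before introduction of the study and will continue regardless of study enrollment status".

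The statistical section sets up a 2 × 2 table of the lateral flow immunoassay (LFI) against culture and names sensitivity as the measure.

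**The concern.** A test meant for suspected plague should have its false-positive rate measured in patients who look as if they have plague but do not. If a second stream of patients came from programs unrelated to plague, the culture-negative column of the table could fill with people in whom a false positive is less likely. Specificity calculated from the pooled table would then flatter the test, and the data are intended for an FDA submission.

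The same patients would use places under the ceiling of 300. Reaching that number would not mean that 300 suspects had been tested, and fewer confirmed cases would leave sensitivity less precise. They would also lack the mandated bubo or sputum sample needed for the paired comparison.

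The text gives some ground for the worry. Declaration of every suspect is compulsory. If the suspect criterion binds everyone, each participant is already in the plague reporting system, and a second source seems to have little purpose. If it does not bind everyone, a route exists that no other section describes. The priority rule orders the sources without limiting either.

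**Working it through.** **Step 1: which reading does the text support?**

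- The source clause says where patients may come from. It does not waive a criterion.
- The suspect-case item and the symptom item stand in the same list as the source clause.
- The section on consenting participants opens the consent process only to someone who meets the inclusion criteria.
- The operational sequence is a physician's suspicion, a declaration form with samples, treatment, an alert to the field team, and then enrolment under a TLO number. Every step presupposes a suspect.
- The clause keeps a use on this reading. A patient can come to notice through another program, be judged a suspect and then be declared. Source and declaration status are different things, so ranking sources can still make sense.

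With the criteria applied jointly, the number of non-suspects, *m*, is 0, and neither feared effect arises.

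**Step 2: what would the other reading cost?**

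The protocol gives no confirmation rate, accuracy or expected mix of sources, and does not derive the 300. Everything below except the 300 is therefore assumed: non-suspects are all culture-negative, 30% of suspects are confirmed, sensitivity is 80%, and specificity is 90% in suspects and 99% in non-suspects.

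- Confirmed cases = 0.3 × (300 − *m*)
- Culture-negative suspects = 0.7 × (300 − *m*)
- Pooled specificity = (culture-negative suspects × 0.90 + *m* × 0.99) / (culture-negative suspects + *m*)

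| *m* | Culture-negative suspects | Pooled specificity | Confirmed cases | Exact 95% CI at 80% sensitivity |
|---|---|---|---|---|
| 0 | 210 | 189/210 = 90.0% | 90 | 72/90: 70.2–87.7% |
| 50 | 175 | 207/225 = 92.0% | 75 | 60/75: 69.2–88.4% |
| 100 | 140 | 225/240 = 93.8% | 60 | 48/60: 67.7–89.2% |
| 150 | 105 | 243/255 = 95.3% | 45 | 36/45: 65.4–90.4% |

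If specificity in suspects is 95%, pooled values are 95.9%, 96.7% and 97.4% for *m* = 50, 100 and 150. If it is 90% in both groups, pooled specificity stays at 90.0% throughout. With *m* = 100, the 90%/99% pair and confirmation from 10% to 50%, it runs from 93.2% to 94.5%.

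**Step 3: do the conditions for harm hold?**

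- *Specificity.* The rise comes entirely from the assumed 90%/99% gap. The protocol does not support that gap, and the symptom criterion works against it, since a participant from any source must still have a plague-like symptom.
- *Sensitivity.* Its denominator is culture-positive participants. Culture-negative non-suspects are not in it and cannot bias it.
- *Lost cases.* The fall from 90 confirmed cases requires suspects to be turned away because others hold their places. The priority rule favours the plague surveillance program. When suspects are few, others fill places that would have stayed empty, and no confirmed case is lost. Even with 50 places displaced, the interval moves only from 70.2–87.7% to 69.2–88.4%.

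**Step 4: could analysts separate the groups?**

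Every declared suspect has a declaration form completed by the physician, and study data are tracked by TLO number. Restricting a table to declared suspects therefore appears feasible from records the protocol already requires.

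**The case for a change.** The best argument for acting is that eligibility is fixed at enrolment. A statistical analysis plan can define the analysis population, but it cannot give back places already used, and it can stratify by source only if source was recorded. The list mixes alternatives (adults, children) with requirements and permissions, so it does not say in so many words that the suspect criterion governs every source. The symptom item is loose, since fever or chills is enough. A clarifying sentence would cost almost nothing.

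Part of this stands: the term is undefined, there is no cap, and the wording could be clearer. The flat layout is weak evidence, though, because nesting may have been lost when the text was extracted; the guardian items plainly belong under children. Places are lost only if the field team enrols someone who fails a stated criterion. The choice of analysis population, and any separate reporting, commonly belongs to the statistical analysis plan, which is not at hand. A pooled specificity could be read from the 2 × 2 table, but the protocol does not name specificity as its measure.

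**Conclusion.** The concern does not hold as a flaw in the plan. Followed as written, with the inclusion criteria applied together, the protocol enrols suspects only, and the effect on specificity and on the number of confirmed cases is nil. The harm needs a reading that sets aside a stated criterion. A specificity shift also needs an assumed difference between groups, and a loss of cases needs suspects to be displaced against the priority rule. Under those assumptions, 50 non-suspects would add 2.0 percentage points to specificity and barely change the sensitivity interval; larger effects need a third to a half of the 300 to be non-suspects, which nothing in the document suggests. An undefined recruitment term remains, a gap that field staff and analysts can fill sensibly from the rest of the protocol. This conclusion rests on the joint reading of the criteria and on the declaration records being available to analysts.
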